## 2. LIST OF ABBREVIATIONS

3D	3 Dimensional
5-FU	5 fluoro-uracil
AE	Adverse events
ANC	Absolute Neutrophil Count
AP/PA	Anterior to Posterior, Posterior to Anterior
APC	Argon Plasma Coagulation
BED	Biologically Equivalent Dose
BID	Twice Daily
CBC	Complete Blood Count
CBCT	Cone Beam Computed Tomography
CDDP	Cisplatin
Chemo	Chemotherapy
CPC	Cancer Protocol Committee
CRT	Chemoradiotherapy
CT	Computed Tomography
CTCAE	Common Terminology Criteria for Adverse Events
CTEP	Cancer Therapy Evaluation Program
CTV	Clinical Tumor Volume
D10cc	Minimum dose to the 10 milliliters of any volume receiving the highest dose
D2cc	Minimum dose to the 2 milliliters of any volume receiving the highest dose
DCI	Duke Cancer Institute
DCIS	Ductal carcinoma in situ
DLT	Dose Limiting Toxicity
Dmax	Maximum dose to any voxel within a volume
DUHS	Duke University Health System
ECOG	Eastern Cooperative Oncology Group
EFRT	Extended Field Radiotherapy
EQD2	Equivalent dose at 2 Gray per fraction
FIGO	International Federation of Gynecology and Obstetrics
G3 or G4	Grade 3 or Grade 4 toxicity
GCP	Good Clinical Practice
GOG	Gynecologic Oncology Group
GTV	Gross Tumor Volume
GU	Genitourinary
GY	Gray
HDR	High Dose Rate
ICRU	International Commission on Radiation Units and Measurement
ID	Identification
IMRT	Intensity Modulated Radiation Therapy (including Volumetric Modulated Arc Therapy)
IRB	Institutional Review Board
KPS	Karnofsky Performance Scale
LDR	Low Dose Rate

LINAC	Linear Accelerator
LRC	Loco-regional control
MRI	Magnetic Resonance Imaging.
MTD	Maximum Tolerated Dose
MV	Megavoltage
NCI	National Cancer Institute
OS	Overall Survival
PA	Para-aortic
PBI	Partial Breast Irradiation
PET	Positron Emission Tomography
PI	Primary Investigator
PTV	Planning Target Volume
NRG	National Surgical Adjuvant Breast and Bowel Project (NSABP), the Radiation Therapy Oncology Group (RTOG), and the Gynecologic Oncology Group (GOG)
SBRT	Stereotactic body radiation therapy
SOC	Safety Oversight Committee
TD5/5	Toxic dose of 5% at 5 years
V18	Partial volume receiving greater than or equal to 18 Gray
WAI	Whole abdominal irradiation
WPRT	Whole Pelvic Radiotherapy

### **3. PROTOCOL SYNOPSIS**

#### **3.1 Purpose:**

This protocol seeks to build on the favorable results of our phase I trial (Pro00015617) by extending our findings to a larger cohort of subjects.

##### **Primary Objective**

1. Determine physician reported rates of good/excellent cosmesis at baseline and 6 months, 1, 2, and 3 years post-treatment as measured by the NRG cosmesis scale (Appendix II).

##### **Secondary Objectives**

1. Determine patient-reported rates of good/excellent cosmesis at baseline and 6 months, 1, 2, and 3 years post-treatment as measured by the NRG cosmesis scale.
2. Assess patient-reported Quality of Life (FACT-B) and patient satisfaction at the same time points.
3. Assess locoregional control in the treated breast relative to historical controls at 10 years.

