**3.5 Selection of Subjects and Sample Size:**

Women ages 60 or older with clinically node-negative, 2cm or less, biopsy proven ductal carcinoma in situ or invasive carcinoma will be considered for this trial. Women age 50-59 with a cT1N0 tumor and a low Oncotype score will also be eligible.

The final sample size is 100 subjects. Up to 150 subjects may be consented in order to enroll the target goal of 100. Given the rapid accrual of our previous trial with similar eligibility (approximately 30/32 subjects over 2 years), we anticipate completion of this trial in 5 years.

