**3.6 Duration of Study:**

Subjects will be on study for approximately 3 years. Thereafter subjects will continue to be followed by the treating medical oncologist and/or radiation oncologist/mid level provider as per standard of care for follow up care.

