## 6. PATIENT ASSESSMENTS

Assessment	Pre-Tx.	Follow-up
Consent	X	
History/Physical	X	X a
Complete Blood Count (no differential)/CMP	X	
Breast imaging (mammogram minimum)	X	X a
Core Biopsy/Fiducial Markers	X b	
Planning MRI	X	
Surgical Excision with Tissue Procurement		X c
Acute Toxicity Evaluation		X d
Cosmetic Evaluation Form/Digital Photographs/QOL	X e	X e
Clinical Outcomes		X a
Serum collection	X f	X f
Urine collection	X g	X g
BRPC Consent prior to surgery		X h

- a. Physical exam by member of oncology team recommended every 4-6 months for 2 years, every 6 months through year 5 and annually years 5-10. Bilateral mammogram recommended at least annually.
- b. Verify placement of a biopsy clip at diagnostic procedure and availability of pre-treatment tissue for correlative science.
- c. Within 10 days of radiation.
- d. Appointment with the Radiation Oncologist/mid level provider 1-2 months after surgery.
- e. At baseline (prior to treatment), six months and one year after treatment and then annually for 2 additional years. Cosmetic assessment to be filled out by both patient and physician/mid level provider. Digital photographs at the same time points and at investigator's discretion.
- f. 2 lavender tubes drawn prior to radiation therapy and post radiation therapy (before surgery)
- g. Urine collected prior to radiation therapy and post radiation therapy (before surgery)
- h. Subjects will be consented to the existing Biospecimen Repository and Processing Core (BRPC) tissue collection protocol which includes safeguards to ensure adequate tissue for diagnostic evaluation and biomarker assessment

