### **6.4 Follow-up Period:**

Follow-up after completion of therapy will follow national guidelines and includes a history and physical every 4-6 months for the 1st 2 years, every 6 months to a year through year 5 and annually through year 10. Mammograms will be obtained at least annually. Other laboratory or radiographic studies will be obtained as directed by patient symptoms or physical exam. Quality of life and cosmetic assessments, physician/mid level provider and patient, will be performed at 6 month, 1 year, and then annually through 3 years of follow-up as will digital photographs. Local regional recurrence will be monitored on protocol at each follow-up visit.

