### 7.3 Statistical Analyses of the Secondary Objectives

(a) The mean of *patient-reported* rate of good/excellent cosmesis, and its 95% CI, will be estimated at baseline and at 6, 12, 24, and 36 months.

(b) Quality of life (FACT-B) and patient satisfaction will be measured at baseline and at 6, 12, 24, and 36 months. For each scale, the mean and its 95% CI's will be estimated at each time point; boxplots will be used to estimate the distribution of these scales at each time point.

(c) Time to local or regional failure will be defined as the time from start of treatment to date of local or regional failure, whichever comes first; distant failures will be ignored; deaths will be censored. Time to distant failure will be defined as the time from start of treatment to date of distant failure; local and regional failures will be ignored; deaths will be censored. The Kaplan Meier method will be used to estimate both of these distributions.

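### The protocol contradicts itself on whether locoregional recurrence is trial data after about year 3, and section 7.3(c) plans no 10-year estimate or historical comparison for secondary objective 3

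*Combined protocol and SAP*

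**What the plan says.** The third secondary objective in section 3.1 is "Assess locoregional control in the treated breast relative to historical controls at 10 years".

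Four places bear on how long recurrence is followed and how it is analysed:

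- Section 3.6: "Subjects will be on study for approximately 3 years". It continues: "Thereafter subjects will continue to be followed by the treating medical oncologist and/or radiation oncologist/mid level provider as per standard of care".
- Section 6.4: history and physical examination "every 6 months to a year through year 5 and annually through year 10", mammography at least yearly, and "Local regional recurrence will be monitored on protocol at each follow-up visit".
- Section 6 table, footnote a, which is attached to the Clinical Outcomes row: examinations are recommended "every 6 months through year 5 and annually years 5-10".
- Section 7.3(c): it defines time to local or regional failure and time to distant failure, then says "The Kaplan Meier method will be used to estimate both of these distributions".

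On the timetable, section 3.5 relies on the accrual of the previous trial: "approximately 30/32 subjects over 2 years), we anticipate completion of this trial in 5 years". Section 6.2 describes the same 5 years as the enrolment period. Section 7.1 records the increase in sample size from 40 to 100, and section 8 mentions an interim analysis of the first 17 patients before the current amendment.

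**The concern.** A 10-year estimate needs women under observation, with recurrence recorded as trial data, up to year 10. Section 3.6 places them off study from about year 3. Section 6.4 keeps recurrence on protocol for another seven years. A data manager who follows 3.6 would close each woman's record after her 36-month cosmesis visit, and outcomes not collected then may be hard to recover later.

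The analysis section does not settle the matter. The objective promises a comparison with historical controls, but the plan stops at drawing a curve. A benchmark chosen once the curve is known would be open to selection. This is the only tumour-control objective above exploratory level, and the October 2025 amendment (section 3.3 D) left it secondary while moving other endpoints to exploratory, partly because there were no prior data on which to base assumptions.

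The accrual forecast is a smaller, separate matter. The 5 years does not follow from the rate offered in its support, so the expected date of the primary endpoint is uncertain as well.

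**Working it through.** **1. Follow-up, section against section.**

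- Section 3.6: on study to about year 3; afterwards standard care, with no end date and no mention of trial data.
- Section 6.4: visits to year 10; its last sentence puts recurrence on protocol at each of them.
- Section 6 table, footnote a: examinations to year 10, but as a recommendation. Its frequency in years 3 to 5 differs slightly from 6.4; that does not change how far follow-up reaches.
- Cosmesis and quality of life: baseline to 36 months in every section that lists them, so the 3 years in 3.6 match that phase.

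If 3.6 governs data collection, every woman is censored near year 3 and nobody is at risk on study at year 10. If 6.4 governs, data run to year 10 and the objective can be estimated. No section ranks the two or sets a data cut-off.

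**2. Analysis.** Section 7.3(a) and (b) specify 95% CIs; 7.3(c) does not. It names no 10-year time point, historical rate, source, margin or comparison. The only reference rate of this kind elsewhere, 75-80% in section 3.3 C, is for cosmesis.

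**3. Precision at 10 years (illustration).** The documents give no locoregional control rate, so the rates here are assumptions. With all 100 women followed to year 10 and x of n = 100 controlled, the exact limits are the 2.5% point of Beta(x, n − x + 1) and the 97.5% point of Beta(x + 1, n − x):

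- 90% control: 0.824 to 0.951
- 95% control: 0.887 to 0.984
- 98% control: 0.930 to 0.998

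Losses to follow-up would widen these. Any comparison is therefore descriptive.

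**4. The 5-year figure.** Inputs: 30 to 32 women in 2 years and target 100 (section 3.5); at least 17 enrolled before the increase (sections 7.1 and 8).

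- Rate: 30/2 = 15 and 32/2 = 16 a year.
- From zero, 5 years gives 5 × 15 = 75 to 5 × 16 = 80 women, so the stated figure is not reproduced.
- Time for 100 from zero: 100/16 = 6.25 to 100/15 = 6.67 years.
- Rate needed for 100 in 5 years: 100/5 = 20 a year.
- Clock started with 17 enrolled: 100 − 17 = 83 remain; 83/16 = 5.19 to 83/15 = 5.53 years. Five years would then bring the total to 17 + 75 = 92 to 17 + 80 = 97.
- Number already enrolled for 5 years to suffice: 100 − 80 = 20 to 100 − 75 = 25.

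The last woman's 36-month assessment falls 3 years after her treatment: 9.25 to 9.67 years from first enrolment, or 8.19 to 8.53 years from a start with 17 enrolled.

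**The case against.** The best defence is that year-10 follow-up is already in the plan. Section 6.4 schedules it and calls recurrence monitoring on protocol, and the section 6 table ties the same span to clinical outcomes. Section 3.6 does not stop follow-up either. It can be read as closing the cosmesis and quality-of-life phase, with recurrence followed for longer. The objective is also secondary, with no test attached, and the sample size is justified only by the precision of the cosmesis rate, so the primary endpoint is untouched.

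Much of this stands. A reader might infer that the 10-year objective cannot be met, or that nobody will be at risk at year 10. The documents do not support that: it follows only if section 6.4 and the section 6 table are set aside. What remains is that 3.6 speaks of being on study without limiting this to cosmesis, and the footnote only recommends visits. The benign reading is plausible but not written down.

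On the timetable, a reader might set the last 36-month or 10-year visit against the stated 5 years and call the plan many years adrift. Section 6.2 describes the 5 years as enrolment, and section 3.5 argues it from accrual, so that comparison mixes different quantities. Nor is a shortfall to 75 or 80 women established: those figures count from zero, at least 17 women were enrolled before the increase to 100, and the start of the clock is not stated. Slower accrual would delay a 10-year estimate, not prevent it.

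**Conclusion.** The contradiction between section 3.6 and section 6 is real and decides whether years 3 to 10 yield trial data. It is a defect of wording with a large possible consequence: under 3.6 the curve ends about seven years short of the objective (10 − 3 = 7), and under 6.4 it does not. Independently of that, the objective as worded is never analysed, because section 7.3(c) contains neither a 10-year estimate with its CI nor anything historical to compare it with. On its own, the missing benchmark would be close to missing detail; the follow-up conflict is what makes correction necessary.

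The accrual error is minor. The like-for-like gap is 6.25 to 6.67 years against 5 if counted from zero, and 5.19 to 5.53 against 5 if counted from 17 enrolled. Both assume that the earlier trial's rate carries over unchanged. With 20 to 25 women already enrolled, the 5 years would be right.

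**What to change.** - **Sections 3.6, 6 and 6.4.** State that cosmesis and quality-of-life participation ends at 3 years, and that recurrence and vital status are collected as trial data through year 10 at the visits already listed. Give the data cut-off for the 10-year analysis. If year-10 collection is not intended, restate objective 3 as 3-year control. The consent form, which I have not seen, should be checked to cover whichever is chosen.
- **Section 7.3(c).** Report Kaplan-Meier locoregional control at 10 years with its 95% CI, set against a historical rate and source fixed before the data are analysed, and label the comparison descriptive.
- **Sections 3.5 and 6.2 (lesser).** Either restate enrolment as about 6.25 to 6.7 years from zero, or give the start point, the number then enrolled and the assumed rate. Say that the 36-month primary endpoint needs 3 more years after the last enrolment.

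The cost is protocol wording and a little yearly chart abstraction at visits already scheduled. The stated timeline becomes less favourable. Treatment and the primary analysis do not change.

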##### **Exploratory Objectives**

1. Ki-67 will be assessed as a measure of tumor response.
2. Assess the impact of radiation on gene expression
3. Assess the impact of radiation on circulating cell-free DNA via serum markers and oxidative stress as measured by urinary biomarkers. Please see Appendix VI for additional detail regarding serum and urine assessment.
4. To review treatment plans, evaluate delivery techniques and assess positioning verification images

##### **Hypotheses**

In this study, we hypothesize that 21Gy can be delivered preoperatively to a large group of subjects with high rates of good/excellent cosmetic outcomes

#### **3.2 Background and Significance:**

In 1990, the National Institutes of Health concluded that breast conservation, conservative surgery followed by radiotherapy, was the preferred treatment for women with early stage breast cancer as no survival advantage was seen in women receiving a more radical and disfiguring mastectomy. As a result, breast conservation consisting of lumpectomy followed by 6 weeks of daily external beam radiotherapy became the standard of care in the United States (US). Treatment typically consisted of 4.5-5 weeks of whole breast treatment followed by a 1-1.5 week boost to the surgical resection cavity. Unfortunately, some women electing to receive breast conserving surgery struggled to complete the recommended radiotherapy. Patterns of care studies demonstrated that older women, and those living in low-income regions or far from radiotherapy centers, often omitted radiotherapy altogether. Numerous studies have demonstrated that the local recurrence rates in these women receiving conservative surgery alone are unacceptably high.

As a result, there has been much interest in development of a more convenient alternative to standard radiotherapy. Recently, robust data has documented that a 3 week course of whole breast radiotherapy is an efficacious and safe alternative to standard therapy. Much additional work has been done on partial breast irradiation (PBI), rapid treatment of the tumor bed plus a small margin of normal tissue, delivered in 1 to 5 days. Several techniques have evolved to deliver PBI: low-dose rate (LDR) brachytherapy, high-dose rate (HDR) brachytherapy via intracavitary applicator, external beam radiotherapy and intra-operative radiation. LDR brachytherapy has the most extensive follow-up but has not been widely adopted due to the significant technical expertise required for accurate and efficient delivery. Intracavitary and external beam radiotherapy, the two most common forms of partial breast irradiation, are widely available and relatively easily applied. However, treatment is still intensive, requiring 10 treatments delivered 6 hours apart over five days. Furthermore, though most preliminary data suggest comparable rates of local control, increasing data are accumulating that soft tissue fibrosis and cosmetic outcomes may be suboptimal with the popular external beam technique. Several investigators have suggested that this may be attributable to the large volume of tissue treated to high doses in the post-operative setting.

We proposed a phase I trial evaluating pre-operative radiation as a solution to this issue. Delivery of radiation pre-operatively to the intact tumor allows more precise targeting of a much smaller volume than a large post-operative seroma. Furthermore, the highly conformal nature of stereotactic radiosurgery is ideal to minimize the volume of uninvolved breast tissue and skin receiving high-dose radiation during PBI, two advantages of the intra-operative technique that likely contribute to the acceptable outcomes seen with this single dose therapy. However, in contrast to intra-operative treatment which requires significant investment in costly intra-operative radiation equipment and a great deal of flexibility in operating room scheduling, most radiation facilities have the capability to treat with stereotactic radiosurgery. This high precision, conformal, rapid, linear accelerator based external beam partial breast irradiation captures the appeal of single-dose intra-operative treatment but in a setting that is widely accessible.

Therefore, we set out to determine the maximally tolerated dose of pre-operative radiation in our previous phase I trial. Our target dose was 21Gy, the dose established as effective in intraoperative partial breast trials. Our results have been positive thus far, with only one locoregional recurrence and no dose-limiting acute toxicities despite escalation to 21Gy. Long-term toxicities at a median follow-up of 3 years are similar to expected toxicities with standard therapy. As expected, the volume of breast receiving prescription dose was vastly decreased compared to post-operative treatment. In this study, we hypothesize that 21Gy can be delivered preoperatively to a larger group of subjects with high rates of good/excellent cosmetic outcomes.

### **3.3 Rationale:**

Rationale for single-fraction preoperative technique

We propose in this trial to build on the favorable results of our phase I trial by extending our findings to a larger cohort of subjects. The preoperative approach has several advantages:

- 1) a small intact breast tumor results in significantly less uninvolved breast tissue receiving high radiation doses which likely decreases toxicity;
- 2) more accurate targeting of the high-risk areas of subclinical disease surrounding the tumor is possible,
- 3) smaller treatment volumes are amenable to dose escalation which can further accelerate treatment and improve accessibility for subjects,
- 4) this technical approach is widely utilized in other tumor sites and can be delivered at most radiation facilities
- 5) the pre-operative approach provides a novel opportunity to study breast cancer radiation response.

#### A. Rationale for magnetic resonance imaging (MRI) treatment planning

Target delineation has always been highly subjective in the post-lumpectomy setting. The tumor bed is currently defined as the area of architectural distortion plus surgical clips. Defining this area is subject to inherent variability depending on the bias of the treating physician. Pre-operative assessment of the tumor should certainly improve delineation of the target and the surrounding area at risk. However, the typical tools used for defining breast tumors, mammography and ultrasound, cannot currently be used in conjunction with radiation planning software. CT is commonly used for radiation treatment planning but, as we noted in our phase I trial, does not facilitate clear target delineation. MRI, on the other hand, clearly identifies the tumor and can be used in conjunction with radiation treatment planning software.

#### B. Rationale for patient selection

Numerous trials have demonstrated that local recurrence rates are unacceptably high after lumpectomy alone in all but the elderly population with small, node negative, estrogen-receptor positive tumors. Published data establishing partial breast techniques have demonstrated low local recurrence rates in conjunction with careful patient selection. Those subjects felt to be suitable for partial breast treatment outside the setting of a clinical trial, as defined by the ASTRO consensus statement will be eligible for this study

#### C. Rationale for endpoints

Clinical data suggests that ER+ breast cancers have a larger proportional benefit from radiation than their ER- counterparts. However, clinical assessment of radiation response (aside from long-term follow-up of local control) is rarely observed as radiation is typically delivered in the post-operative setting after resection of gross disease. As a result, tumor and normal tissue radiation response remain relatively poorly understood. Markers capable of predicting radiation response are rare indeed. Therefore, if biologic markers of radiation response could be identified in a subset of subjects, these clinical markers could be used in future clinical trials to explore the impact of alternative total doses, dose per fraction or concurrent therapy.

In addition, two large randomized trials have documented less toxicity with intraoperative radiation at a single dose of 21Gy as compared to standard whole breast radiotherapy. However, this technique does have the critical advantage of delivering radiation to the subcutaneous tissue and minimizing dose to the overlying skin. Pre-operative treatment must necessarily be given with the skin intact. Fibrosis and skin thickening in this area could contribute to suboptimal cosmesis. In our phase I trial, there were

no dose-limiting acute toxicities. In addition, all 29 subjects treated with only 21Gy of radiation (3 subjects received post-operative radiation for high-risk features) had good or excellent outcomes. However, these promising early outcomes must be confirmed in a larger group of subjects with diverse tumor locations and radiation plans. We would expect a rate of good/excellent cosmetic outcomes at 3 years comparable to those seen in the clinical trials evaluating short-course whole breast radiation (75-80% at 3 years). Local control will also be carefully collected and gathered as a secondary endpoint.

